3.2 Randomization Procedure

A randomization list will be produced using a validated system that automates the random assignment of treatment arms to randomization numbers in the specified ratio. At Visit 2, eligible subjects will be given the lowest available randomization number. This number assigns the patient to one of the treatment arms.

3.3 Study Medication

The blinded study medication will consist of:

Evolocumab 420 mg SC QM

Matching Placebo SC QM

The study will utilize the SureClick® auto-injection formulation of evolocumab (formulated with and without the active ingredient). Three doses (140mg per dose) will be administered at each time point.

3.4 Blinding

The identity of the treatments will be concealed by the use of matching placebo to the study drug that are identical in packaging, labeling, appearance and schedule of administration.

3.5 Premature Interruption or Withdrawal from the Study

3.5.1 Premature Interruption of Study Treatment

Subjects have the right to discontinue study treatment for any reason. However, unless they withdraw consent and are no longer willing to participate, they should be followed by telephone calls for the remainder of the trial and all serious events must be reported, regardless of whether or not the event is of cardiovascular origin or occurs under the care of another physician or institution.

In case of a temporary interruption of study treatment, all efforts should be made to re-institute study treatment as soon as the clinical condition of the subject has stabilized based on the judgment of the Investigator.

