- m) Known active infection or major hematologic, renal, metabolic, gastrointestinal or endocrine dysfunction in the judgment of the investigator
- n) Diagnosis of deep vein thrombosis or pulmonary embolism or major surgical procedures within 3 months prior to randomization
- o) Unreliability as a study participant based on the investigator's (or designee's) knowledge of the subject (e.g. alcohol or other drug abuse)
- p) Currently enrolled in another investigational device or drug study, or less than 30 days since ending another investigational device or drug study(s), or receiving other investigational agent(s)
- q) Female subject who has either (1) not used at least 1 highly effective method of contraception for at least 1 month prior to screening or (2) is not willing to use such a method during treatment and for an additional 15 weeks after the end of treatment, unless the subject is sterilized or postmenopausal;
 - a. Menopause is defined as: 12 months of spontaneous and continuous amenorrhea in a female \geq 55 years old or 12 months of spontaneous and continuous amenorrhea with a follicle-stimulating hormone (FSH) level > 40 IU/L (or according to the definition of "postmenopausal range" for the laboratory involved) in a female < 55 years old unless the subject has undergone bilateral oophorectomy
 - b. Highly effective methods of birth control include: not having intercourse or using birth control methods that work at least 99% of the time when used correctly and include: birth control pills, shots, implants, or patches, intrauterine devices (IUDs), tubal ligation/occlusion, sexual activity with a male partner who has had a vasectomy, condom or occlusive cap (diaphragm or cervical/vault caps) used with spermicide
- r) Subject who is pregnant or breast feeding, or planning to become pregnant during treatment and/or within 15 weeks after the end of treatment
- s) Use of a PCSK9 inhibitor within 10 weeks from screening visit
- t) Subject who has any kind of disorder that, in the opinion of the investigator, may compromise the ability of the subject to give written informed consent and/or to comply with all required study procedures
- u) Malignancy except non-melanoma skin cancers, cervical or breast ductal carcinoma in situ within the last 5 years

- v) Subject who has known sensitivity to any of the products or components to be administered during dosing

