3. STUDY DESIGN

3.1. Study Overview

This is a double-blind, randomized, placebo-controlled, parallel group Phase IV study with two treatment arms: evolocumab SC 420 mg/dL QM or matching placebo. The population will include men and women of non-child-bearing potential with documented CAD and type 2 diabetes.

Approximately 100 subjects will be screened in order to keep 40 subjects to complete the study. Subjects will be followed for 12 weeks during the treatment phase, maintaining the double-blind throughout. Assessments of ACUTE and SHORT-TERM effects of PCSK9 inhibition with evolocumab on biocellular markers of endothelial function will be measured at baseline, Week 2, and Week 12. Safety assessments will be undertaken at each study visit. Subjects whose maximally tolerated dose of statin is no type or dose (i.e. determined to be statin intolerant by primary investigator) must be randomized fairly between 2 treatment arms to prevent selection bias.

Subjects should continue on their stable dose of anti-hyperglycaemic therapies during the course of the study. However, it is important that the haemoglobin A1c (HbA1c) does not rise above 10% and that the patient does not develop severe hypoglycaemia or frequent episodes of mild-moderate hypoglycaemia, as defined by the Canadian Diabetes Association 2008 Clinical Practice Guidelines for the Prevention and Management of Diabetes.¹³

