3.5.2 Withdrawal of Consent

Subjects may decide to fully or partially withdraw their consent to participate in the study. At that point, it should be established, whether the withdrawal is related to study treatment, further assessments, or any further involvement in the study. If the withdrawal is primarily related to study treatment or specific assessments, subjects should be encouraged to continue follow-up by telephone calls and to attend all other subsequent study assessments. Reports on serious events should be collected until completion of the study for all withdrawals, unless the subject objects to such follow-up.

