4 SCHEDULE OF STUDY PROCEDURES

Screening assessments and study procedures outlined in this section and in Table 1 can only be performed after obtaining written informed consent.

All on-study visits and dosing should be scheduled from Day 1 (first IP administration). For example, the Week 2 visit is 2 calendar weeks after the study Day 1 visit, which corresponds to study Week 2. When it is not possible to perform the study visit at the specified time point, the visit should be performed within the visit window specified in Table 1. If a study visit is missed or late, including visits outside the visit window, subsequent visits should resume on the original visit schedule. Missed assessments at prior visits should not be duplicated at subsequent visits. With the exception of screening, all study procedures for a visit should be completed on the same day if possible.

Visit 1: Screening

- Written informed consent
- Demographics
- Medical history
- Vital signs
- 12 lead ECG measurement
- Concomitant therapy
- Dietary instruction; medication compliance reminder
- Physical examination
- Body height, waist circumference
- Body weight
- Seattle Angina Questionnaire 7 (SAQ7)
- Laboratory assessments: TSH, hematology (CBC), blood chemistry (creatinine/eGFR and electrolytes), Liver Function Tests (ALT, AST), creatinine/eGFR, HbA_{1c}, local lipid panel, urine albumin to creatinine ratio (ACR), urine pregnancy test (if female of child bearing potential)

Visit 2 (Randomization) 7-28 days after Screening

- Review for AEs/SAEs/CV events
- Concomitant therapy
- Vital signs
- Dietary instruction; medication compliance reminder
- Randomization
- Seattle Angina Questionnaire 7 (SAQ7)
- Laboratory assessments: fibrinogen, whole blood viscosity analysis, NMR lipoprotein subclass analysis, Apo B, lipoprotein (a), biocellular marker analysis, Oxidized lipid Analysis
- DNA/mRAN test for lipoprotein and inflammatory polymorphisms that may influence the response to therapy (the specimens will be stocked at site and the tests will be performed later).
- SC IP administration, QM (in-clinic) and 30 minute post-injections observation

Visit 3 (Week 2) ±4 days

- Review for AEs/SAEs/CV events
- Concomitant therapy
- Vital signs

- Dietary instruction; medication compliance reminder
- Seattle Angina Questionnaire 7 (SAQ7)

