- Laboratory assessments: hematology (CBC), blood chemistry (creatinine/eGFR, electrolytes), Liver Function Tests (ALT/AST), fibrinogen, whole blood viscosity analysis, NMR lipoprotein subclass analysis, Apo B, lipoprotein (a), biocellular marker analysis, Oxidized lipid Analysis

Visit 4 (Week 4) ±7 days

- Review for AEs/SAEs/CV events
- Concomitant therapy
- Vital signs
- Dietary instruction; medication compliance reminder
- Seattle Angina Questionnaire 7 (SAQ7)
- SC IP administration, QM (in-clinic) and 30 minute post-injections observation

Visit 5 (Week 8) ±7 days

- Review for AEs/SAEs/CV events
- Concomitant therapy
- Vital signs
- Dietary instruction; medication compliance reminder
- Seattle Angina Questionnaire 7 (SAQ7)
- SC IP administration, QM (in-clinic) and 30 minute post-injections observation

Visit 6 (Week 12) ±7 days

- Body height, waist circumference
- Body weight
- Review for AEs/SAEs/CV events
- Concomitant therapy
- Dietary instruction; medication compliance reminder
- Seattle Angina Questionnaire 7 (SAQ7)
- Laboratory assessments: hematology (CBC), blood chemistry (creatinine/eGFR, electrolytes), Liver Function Tests (ALT/AST), fibrinogen, whole blood viscosity analysis, NMR lipoprotein subclass analysis, Apo B, lipoprotein (a), biocellular marker analysis, Oxidized lipid Analysis

Table 1. Schedule of Assessments

Schedule of Assessments	Screening	Baseline/ Randomization	Week 2	Week 4	Week 8	Week 12
Visit Number	1	2	3	4	5	6
Visit Window		± 7-28 Days	± 4 Days	± 7 Days	± 7 Days	± 7 Days
Informed consent	X					
Demographics & Medical history	X					
Vital signs (HR, BP)	X	X	X	X	X	X
ECG	X					
Review for AEs/SAEs/CV events		X	X	X	X	X
Concomitant therapy	X	X	X	X	X	X
Dietary instruction; medication compliance reminder	X	X	X	X	X	
Physical examination	X					
Body height, waist circumference	X					X
Body weight	X					X
Seattle Angina Questionnaire 7 (SAQ7)	X	X	X	X	X	X
Placebo Injection	X					
Laboratory Analyses:						
TSH	X					
Hematology (CBC)	X		X			X
Chemistry (creatinine/eGFR, electrolytes)	X		X			X
Liver Function Tests (AST, ALT)	X		X			X
Urine albumin to creatinine ratio (ACR)	X					X
HbA1c	X					
Local Lipid Panel	X					
Urine pregnancy (if applicable)	X					
Fibrinogen		X	X			X
lipoprotein(a), Apo B		X	X			X
Whole Blood Viscosity Analysis		X	X			X
NMR Lipoprotein Subclass Analysis		X	X			X
Biocellular Marker Analysis		X	X			X
Oxidized lipid Analysis		X	X			X
DNA/mRNA test		X				
Randomization		X				

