7.1 Sample Size Estimation

The goal of this study is to estimate biologically plausible effects as a result of PCSK9 inhibition in a population of patients with type 2 diabetes and microvascular dysfunction. As a result, this will be treated as a “signal” finding trial – and used as preliminary data to support a formal sample size estimation for a larger clinical trial. We anticipate that 40 subjects will be required to provide sufficient data to adequately identify robust changes in the large range of biocellular markers being assessed.

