7.2 Statistical Analysis

As we seek to address both early and late changes in biocellular responses as a result of PCSK9i, we will compare changes between week 2 and week 12 with baseline. We will also compare week 2 with week 12 to identify how the expected rheological changes may impact biocellular responses.

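### Section 3.5.1 gives subjects who stop study drug with consent intact only telephone follow-up, so their Week 12 marker samples can be lost to the ITT estimate; aligning it with 3.5.2 is a cheap improvement

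*Combined protocol and SAP*

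**What the plan says.** Section 3.5.1 covers subjects who discontinue study treatment for any reason. Its follow-up rule is that "unless they withdraw consent and are no longer willing to participate, they should be followed by telephone calls for the remainder of the trial", and serious events must be reported. It neither requires nor forbids the marker visits.

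Section 3.5.2 has a different trigger, full or partial withdrawal of consent. Where the withdrawal mainly concerns study treatment or particular assessments, "subjects should be encouraged to continue follow-up by telephone calls and to attend all other subsequent study assessments".

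Section 4 says that after a missed or late visit "subsequent visits should resume on the original visit schedule". It does not say whether subjects off drug keep attending. Table 1 has no separate row or footnote for them.

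Under section 3.1, "biocellular markers of endothelial function will be measured at baseline, Week 2, and Week 12". The Week 12 samples come from a blood draw at Visit 6. Study drug is given at Visit 2 (Day 1), Visit 4 (Week 4) and Visit 5 (Week 8), each listed as "SC IP administration, QM (in-clinic) and 30 minute post-injections observation".

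On analysis, section 7.2 states that "we will compare changes between week 2 and week 12 with baseline", and adds a comparison of Week 2 with Week 12. Section 7.3 specifies a baseline-adjusted ANCOVA on the ITT principle, puts the emphasis on estimates over tests, and gives no method for missing values. Section 7.1 says the results will be "used as preliminary data to support a formal sample size estimation for a larger clinical trial".

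**The concern.** A telephone call cannot supply a blood sample. Read side by side, the two follow-up sections give an odd result: a subject who partly withdraws consent is encouraged to come to visits, while one who keeps full consent and only stops the injections is assigned calls.

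An ITT estimate at Week 12 needs Week 12 values from everyone randomised. If subjects who stopped are not sampled, the active arm at Week 12 consists of those still on drug. The ANCOVA on available data then moves away from the effect of assignment and towards the effect in those who stayed on treatment. The Week 2 versus Week 12 comparison would also rest on different sets of subjects at the two times. Because section 7.3 reads the trial through its point estimates, and section 7.1 passes them on to a larger trial, bias and precision are what matter here, more than a formal test.

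Week 2 is less exposed. The second dose is not due until Week 4, so a Week 2 sample is at risk only for someone who discontinues in the first two weeks.

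**Working it through.** **Which text applies to whom**

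| Subject | Section | Follow-up named |
|---|---|---|
| Stops drug, consent intact | 3.5.1 | Telephone calls, serious-event reporting |
| Partly withdraws consent, mainly over treatment or specific assessments | 3.5.2 | Telephone calls and encouragement to attend other assessments |
| Misses a visit or comes late | 4 | Later visits on the original schedule |

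The first row is the gap.

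**Time since last dose at Week 12, from the schedule**
- All doses taken: 12 − 8 = 4 weeks.
- Stopped before the Week 8 dose: 12 − 4 = 8 weeks.
- Stopped before the Week 4 dose: 12 weeks.

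A subject who discontinues after the Week 8 dose has missed no dose.

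**Inputs**
- From the documents: 40 subjects (3.1, 7.1); baseline-adjusted ANCOVA, ITT (7.3).
- Assumed, because the documents do not give them: 1:1 allocation with 20 per arm; p, the share of the active arm that stops; m, the share of those who miss Week 12; k, the share of the effect they keep at Week 12. Subjects who stop are taken to be otherwise like the rest.

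The plan states no effect size, SD, power or dropout rate, so there is no figure of its own to reproduce.

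**Bias.** With the on-drug effect set to 1:
- ITT effect = 1 − p(1 − k)
- Effect among those sampled = 1 − [p(1 − m)/(1 − pm)](1 − k)
- Overstatement = ratio of the second to the first, minus 1

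Example, p = 0.10, m = 1, k = 0: ITT effect 0.90, sampled effect 1.00, overstatement 1/0.90 − 1 = 11.1%.

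| p | m = 1, k = 0.5 | m = 1, k = 0 | m = 0.5, k = 0.5 | m = 0.5, k = 0 |
|---|---|---|---|---|
| 5% (1 of 20) | 2.6% | 5.3% | 1.3% | 2.6% |
| 10% (2 of 20) | 5.3% | 11.1% | 2.5% | 5.3% |
| 20% (4 of 20) | 11.1% | 25.0% | 4.9% | 11.1% |

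If those who stop keep the whole effect (k = 1), the overstatement is zero.

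**Bias against random error.** Half-width of the 95% CI in SD units = t(0.975, N − 3) × √[(1/n₁ + 1/n₂)(1 − r²)], with N = n₁ + n₂ and r the baseline correlation (assumed 0 to 0.5).
- 20 versus 20: 0.641 (r = 0), 0.555 (r = 0.5).
- 16 versus 20, as in the extreme case: t(0.975, 33) × √0.1125 = 0.68 (r = 0); × √0.75 = 0.59 (r = 0.5).

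For an assumed on-drug effect of 0.80 SD and m = 1, the bias is 0.80 × p(1 − k):
- p = 0.05, k = 0.5: 0.02 SD.
- p = 0.10, k = 0: 0.08 SD.
- p = 0.20, k = 0: 0.16 SD, which is 0.16/0.68 = 23% to 0.16/0.59 = 27% of the half-width.

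**Precision.** If samples are lost in both arms (r = 0), the half-width goes from 0.64 SD to 0.68 SD at 10% loss (18 per arm) and 0.72 SD at 20% loss (16 per arm).

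**The case against.** The strongest reply is that this is an ambiguity between sections and not a rule that loses samples. A subject who chooses to stop injections could well be handled as a partial withdrawal under 3.5.2. That section pairs calls with attendance, so the calls in 3.5.1 can be read as a minimum. Table 1 exempts nobody, and section 4 brings subjects back to schedule after a missed visit. It is also a signal-finding trial about biological effects, where drift towards the on-drug effect does limited harm.

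Much of this stands. Loss is possible and not certain, and a sensible site may keep everyone attending. But 3.5.2 depends on withdrawal of consent, so it does not reach a subject taken off drug for another reason, such as an adverse event. Nothing elsewhere tells a site to bring that subject in. A site that only telephones is following the text.

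Two stronger readings are tempting, and the documents support neither.
- A reader might infer that a subject 12 weeks past the last dose has lost the effect, because prior users are excluded for "Use of a PCSK9 inhibitor within 10 weeks from screening visit". That interval runs to screening, and the baseline marker sample is drawn 7-28 days later, so the minimum gap to that sample is about 11-14 weeks. Twelve weeks lies inside that range. The rule concerns eligibility and does not measure marker decay.
- A reader might convert the overstatement into lost power for the larger trial. Section 7.1 says only that these data will support its sample size estimation. It does not say that this point estimate will be used directly, or that the stopping pattern will be the same.

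**Conclusion.** The gap in 3.5.1 is real, and it matters because section 7.3 claims an ITT estimate at a visit that these subjects are not told to attend. Its size cannot be known from the documents. With 5-10% of the active arm stopping and all of them unsampled, the overstatement is about 3-5% if half the effect is kept and 5-11% if none is. It is smaller if some attend, and nil if nobody stops or the effect persists in full.

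The 25% figure is a bound and not an expectation. It needs 20% stopping, every one of them missing Week 12, and every one losing the whole effect. Even then the bias is about a quarter of the CI half-width, so random error dominates with 40 subjects. A reader might infer that the trial's validity is at stake; these figures do not support that. This is a cheap improvement, worth making because blood not drawn at Week 12 cannot be recovered later.

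**What to change.** Reconcile 3.5.1 with 3.5.2. State in 3.5.1 that subjects who stop study drug without withdrawing consent are asked to attend the remaining scheduled marker visits, in particular Week 12, for all planned samples, with telephone contact only if they decline. In 7.3, report by arm how many subjects stopped and how many of those have a Week 12 sample.

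The cost is one sentence in each section. Visit 6 and its assays already exist, so no visit or test is added. The downside is that a few subjects off drug are asked to come to an existing visit; some may decline, so losses are reduced and not ruled out. The change concerns sampling only, and not when study drug is stopped or restarted.

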3.5.2 Withdrawal of Consent

Subjects may decide to fully or partially withdraw their consent to participate in the study. At that point, it should be established, whether the withdrawal is related to study treatment, further assessments, or any further involvement in the study. If the withdrawal is primarily related to study treatment or specific assessments, subjects should be encouraged to continue follow-up by telephone calls and to attend all other subsequent study assessments. Reports on serious events should be collected until completion of the study for all withdrawals, unless the subject objects to such follow-up.

4 SCHEDULE OF STUDY PROCEDURES

Screening assessments and study procedures outlined in this section and in Table 1 can only be performed after obtaining written informed consent.

All on-study visits and dosing should be scheduled from Day 1 (first IP administration). For example, the Week 2 visit is 2 calendar weeks after the study Day 1 visit, which corresponds to study Week 2. When it is not possible to perform the study visit at the specified time point, the visit should be performed within the visit window specified in Table 1. If a study visit is missed or late, including visits outside the visit window, subsequent visits should resume on the original visit schedule. Missed assessments at prior visits should not be duplicated at subsequent visits. With the exception of screening, all study procedures for a visit should be completed on the same day if possible.

Visit 1: Screening

- Written informed consent
- Demographics
- Medical history
- Vital signs
- 12 lead ECG measurement
- Concomitant therapy
- Dietary instruction; medication compliance reminder
- Physical examination
- Body height, waist circumference
- Body weight
- Seattle Angina Questionnaire 7 (SAQ7)
- Laboratory assessments: TSH, hematology (CBC), blood chemistry (creatinine/eGFR and electrolytes), Liver Function Tests (ALT, AST), creatinine/eGFR, HbA_{1c}, local lipid panel, urine albumin to creatinine ratio (ACR), urine pregnancy test (if female of child bearing potential)

Visit 2 (Randomization) 7-28 days after Screening

- Review for AEs/SAEs/CV events
- Concomitant therapy
- Vital signs
- Dietary instruction; medication compliance reminder
- Randomization
- Seattle Angina Questionnaire 7 (SAQ7)
- Laboratory assessments: fibrinogen, whole blood viscosity analysis, NMR lipoprotein subclass analysis, Apo B, lipoprotein (a), biocellular marker analysis, Oxidized lipid Analysis
- DNA/mRAN test for lipoprotein and inflammatory polymorphisms that may influence the response to therapy (the specimens will be stocked at site and the tests will be performed later).
- SC IP administration, QM (in-clinic) and 30 minute post-injections observation

Visit 3 (Week 2) ±4 days

- Review for AEs/SAEs/CV events
- Concomitant therapy
- Vital signs

- Dietary instruction; medication compliance reminder
- Seattle Angina Questionnaire 7 (SAQ7)
- Laboratory assessments: hematology (CBC), blood chemistry (creatinine/eGFR, electrolytes), Liver Function Tests (ALT/AST), fibrinogen, whole blood viscosity analysis, NMR lipoprotein subclass analysis, Apo B, lipoprotein (a), biocellular marker analysis, Oxidized lipid Analysis

Visit 4 (Week 4) ±7 days

- Review for AEs/SAEs/CV events
- Concomitant therapy
- Vital signs
- Dietary instruction; medication compliance reminder
- Seattle Angina Questionnaire 7 (SAQ7)
- SC IP administration, QM (in-clinic) and 30 minute post-injections observation

Visit 5 (Week 8) ±7 days

- Review for AEs/SAEs/CV events
- Concomitant therapy
- Vital signs
- Dietary instruction; medication compliance reminder
- Seattle Angina Questionnaire 7 (SAQ7)
- SC IP administration, QM (in-clinic) and 30 minute post-injections observation

Visit 6 (Week 12) ±7 days

- Body height, waist circumference
- Body weight
- Review for AEs/SAEs/CV events
- Concomitant therapy
- Dietary instruction; medication compliance reminder
- Seattle Angina Questionnaire 7 (SAQ7)
- Laboratory assessments: hematology (CBC), blood chemistry (creatinine/eGFR, electrolytes), Liver Function Tests (ALT/AST), fibrinogen, whole blood viscosity analysis, NMR lipoprotein subclass analysis, Apo B, lipoprotein (a), biocellular marker analysis, Oxidized lipid Analysis

Table 1. Schedule of Assessments

Schedule of Assessments	Screening	Baseline/ Randomization	Week 2	Week 4	Week 8	Week 12
Visit Number	1	2	3	4	5	6
Visit Window		± 7-28 Days	± 4 Days	± 7 Days	± 7 Days	± 7 Days
Informed consent	X					
Demographics & Medical history	X					
Vital signs (HR, BP)	X	X	X	X	X	X
ECG	X					
Review for AEs/SAEs/CV events		X	X	X	X	X
Concomitant therapy	X	X	X	X	X	X
Dietary instruction; medication compliance reminder	X	X	X	X	X	
Physical examination	X					
Body height, waist circumference	X					X
Body weight	X					X
Seattle Angina Questionnaire 7 (SAQ7)	X	X	X	X	X	X
Placebo Injection	X					
Laboratory Analyses:						
TSH	X					
Hematology (CBC)	X		X			X
Chemistry (creatinine/eGFR, electrolytes)	X		X			X
Liver Function Tests (AST, ALT)	X		X			X
Urine albumin to creatinine ratio (ACR)	X					X
HbA1c	X					
Local Lipid Panel	X					
Urine pregnancy (if applicable)	X					
Fibrinogen		X	X			X
lipoprotein(a), Apo B		X	X			X
Whole Blood Viscosity Analysis		X	X			X
NMR Lipoprotein Subclass Analysis		X	X			X
Biocellular Marker Analysis		X	X			X
Oxidized lipid Analysis		X	X			X
DNA/mRNA test		X				
Randomization		X				
Investigational Product: SC IP Administration, QM		X		X	X	

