6 MANAGEMENT OF ADVERSE EVENTS

6.1 Adverse Event (AE) Reporting

An adverse event (AE, AEs) is defined as any untoward medical occurrence in a subject who has been administered a pharmaceutical product and which does not necessarily have to have a causal relationship with this treatment. AEs include those reported spontaneously by the subject and those noted incidentally or as observed by the investigator or study staff.

Study staff will assess all AEs that occur during the period from signing of consent until end of study participation and document these in the source documents. Investigators will evaluate any changes in laboratory values and physical symptoms/signs and will determine if the change is clinically significant. If clinically significant and unexpected adverse experiences occur, they will be recorded in the case report form (CRF).

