Any new conditions would be recorded including date of onset, date of resolution, severity (mild, moderate, severe, or serious as defined above) and possible relationship to study drug or procedure. As part of the source notes, follow up clinical assessments, laboratory tests, ECGs and diagnostic imaging related to adverse event should be documented.

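### The rule against repeating missed assessments has no exception for safety laboratories, so a missed Week 2 draw leaves no scheduled on-treatment CBC, chemistry or AST/ALT until Week 12, after all dosing

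*Combined protocol and SAP*

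**What the plan says.** Two sentences in Section 4 govern missed visits. The first keeps later visits on the calendar: "If a study visit is missed or late, including visits outside the visit window, subsequent visits should resume on the original visit schedule". The second covers the content of the missed visit: "Missed assessments at prior visits should not be duplicated at subsequent visits". Neither separates efficacy samples from safety samples.

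The visit lists and Table 1 agree on the safety laboratories. The on-treatment entry is "Laboratory assessments: hematology (CBC), blood chemistry (creatinine/eGFR, electrolytes), Liver Function Tests (ALT/AST), fibrinogen, whole blood viscosity analysis", and it appears at Visit 3 (Week 2) and Visit 6 (Week 12) only. The same safety tests are also done at Screening. They are not among the laboratory tests at Visit 2, when the first administration is given.

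The Week 4 and Week 8 visits each include "SC IP administration, QM (in-clinic) and 30 minute post-injections observation", together with adverse event review, concomitant therapy, vital signs and the angina questionnaire, but no laboratory tests. On dose, Section 3.3 says "Three doses (140mg per dose) will be administered at each time point".

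Section 3.1 adds in general terms: "Safety assessments will be undertaken at each study visit". Section 6.1 says: "Investigators will evaluate any changes in laboratory values and physical symptoms/signs and will determine if the change is clinically significant".

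**The concern.** For time-specific markers the rule is right: a sample taken at Week 4 is not a Week 2 sample and should not stand in for one. A safety laboratory has a different purpose. Its value lies in showing whether the subject has developed an abnormality on treatment, and a late result still answers that question.

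Because the rule makes no distinction, a site that follows it would not draw the missed safety tests at Week 4 or Week 8, although the subject is in clinic for an administration at both. Section 6.1 expects investigators to assess laboratory changes, but for this subject no scheduled on-treatment value exists until dosing is over. A rise in liver enzymes or creatinine, or a fall in a blood count, that causes no symptoms would not prompt an event-related test and could go unseen until Week 12.

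The concern is confined to a draw that is truly missed. A late Week 2 visit can still supply it.

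**Working it through.** The plan gives no figure to reproduce here. The check sets the laboratory schedule against the dosing schedule and counts days after the first administration.

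**Inputs (Section 4, Table 1 and Section 3.3)**
- Screening: 7 to 28 days before Visit 2.
- Week 2: 14 ± 4 days, so 10-18.
- Week 4: 28 ± 7 days, so 21-35.
- Week 8: 56 ± 7 days, so 49-63.
- Week 12: 84 ± 7 days, so 77-91.
- Administrations: Visit 2, Week 4 and Week 8; none at Week 12.
- Dose: 3 auto-injections × 140 mg = 420 mg per administration. Over the study, 3 × 3 = 9 auto-injections and 3 × 420 = 1260 mg. The milligram figures apply to the evolocumab arm only.

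**First scheduled on-treatment safety laboratory**

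| Situation | Days after first administration | Administrations already given | Evolocumab given (active arm) |
|---|---|---|---|
| Week 2 draw done | 10-18 | 1 of 3 | 420 mg |
| Week 2 missed, current rule | 77-91 | 3 of 3 | 1260 mg |
| Week 2 missed, drawn at Week 4 before dosing | 21-35 | 1 of 3 | 420 mg |

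**Time recovered by a catch-up draw, compared with Week 12**
- At Week 4: 77 − 35 = 42 to 91 − 21 = 70 days; at nominal visit days, 84 − 28 = 56.
- At Week 8, if Week 4 is missed too: 77 − 63 = 14 to 91 − 49 = 42 days; nominal 84 − 56 = 28.

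**Gap between scheduled safety values when Week 2 is missed.** No safety laboratories are drawn at Visit 2, so the previous value is the one from Screening: 7 + 77 = 84 to 28 + 91 = 119 days. Scheduled on-treatment draws fall from two to one.

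**What the rule itself adds.** A fully compliant subject already goes 77 − 18 = 59 to 91 − 10 = 81 days between the Week 2 and Week 12 laboratories. The effect of the rule is therefore the loss of the one early check; the long interval that follows is a feature of the schedule for everyone.

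**How many subjects.** The documents give neither a rate of missed Week 2 draws nor a rate of symptomless abnormality. Purely as an assumption, 2.5% to 10% missing Week 2 would be 0.025 × 40 = 1 to 0.10 × 40 = 4 subjects over both arms. With 1:1 allocation, also an assumption because the ratio is not stated, that is 0.5 to 2 on evolocumab.

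**The case against.** The strongest reply is that nothing in the protocol depends on the result. The AST/ALT and eGFR limits apply at screening only, and no hold, stop or dose change is tied to an on-treatment value. This stands, and it limits the harm to later detection. It does not remove the harm: Section 6.1 asks the investigator to judge laboratory changes, and Section 3.5.1 allows for treatment to be interrupted and resumed on clinical judgment. An early abnormal value could therefore be acted on.

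Second, the design accepts a gap of 59-81 days for compliant subjects. That is true, but those subjects have had one on-treatment check first; the affected subject has had none.

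Third, the trigger is narrow. Late visits are foreseen, and same-day completion of procedures is asked for only where possible, so a failed draw might be completed on another day. The wording is advisory and does not bar clinically indicated tests. Section 6.3 expects that "follow up clinical assessments, laboratory tests, ECGs and diagnostic imaging related to adverse event should be documented". All of this stands and shrinks the number affected. But event-related tests need an event, and a symptomless change supplies none. Nor does the general Section 3.1 sentence on safety at each visit create a make-up draw, since the detailed lists for Weeks 4 and 8 contain no laboratories.

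Fourth, a sample taken before the Week 4 administration need not be reported before it, so in practice the result may inform only the third administration. That also stands. Finally, the documents name no hepatic, renal or haematological concern with evolocumab, so the exposure figures describe timing and not risk.

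**Conclusion.** The concern holds as a low-severity point. Followed as written, the rule moves the first scheduled on-treatment safety laboratory from 10-18 days to 77-91 days after the first administration, and from after one administration to after all three, for any subject whose Week 2 draw is truly missed and who has no event-driven or clinically indicated test in between.

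The timing rests only on the stated visit windows and dosing visits. The number of subjects is not known from the documents; 1-4 of 40 is an illustration under an assumed 2.5-10% rate. The loss is one early check for symptomless abnormalities. It does not affect the efficacy comparison.

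**What to change.** In Section 4, limit the no-repeat rule to the time-specific samples: biocellular markers, lipid and lipoprotein tests, fibrinogen and viscosity. Then add one sentence: if the Week 2 CBC, chemistry or AST/ALT are missed, they are drawn at the next attended visit, normally Week 4 and before that visit's administration, with the actual date recorded and the result not reported as a Week 2 value.

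The cost is one sentence and, in the few subjects affected, one delayed blood draw. Section 5.8.1 lists these as local tests, they are already planned, and the subject is attending for dosing anyway. The result will not be a Week 2 value, so any by-visit safety table should show it as an unscheduled or late result.
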